# 2.1.5. Use of Computerized Systems

When clinical observations are entered directly into an investigational site's computerized medical record system (i.e., in lieu of original hardcopy records), the electronic record can serve as the source document if the system has been validated in accordance with Health Authority requirements pertaining to computerized systems used in clinical research. An acceptable computerized data collection system allows

preservation of the original entry of data. If original data are modified, the system should maintain a viewable audit trail that shows the original data as well as the reason for the change, name of the person making the change, and date of the change.

#### 2.2. RETENTION OF RECORDS

Records and documents, including signed ICF/Assents, pertaining to the conduct of this study must be retained by the Investigator for at least 15 years after study completion unless local regulations or institutional policies require a longer retention period. No records may be destroyed during the retention period without the written approval of the Sponsor. No records may be transferred to another location or party without written notification to the Sponsor.

Audio recordings will be maintained on a secure server throughout the duration of the study and will be *retained for at least 15* years after study completion. *No records may be destroyed during the retention period without the written approval of the Sponsor.* 

For countries where Ethics Committees or the Ministry of Health will not approve audio recording of participant interviews, review of the scale worksheets, submitted as part of the assessment source information, will be performed to verify accuracy of scoring and adherence to study conventions.

#### 2.3. STUDY RECORDS

The Investigator must maintain adequate and accurate records to enable the conduct of the study to be fully reconstructed, including but not limited to the protocol, protocol amendments, ICFs, and documentation of IRB/EC and governmental approval.

### 2.3.1. Protocol Amendments

Any substantial protocol amendments will be prepared by the Sponsor. Substantial protocol amendments will be submitted to the IRB/EC and to regulatory authorities (where applicable) in accordance with local regulatory requirements.

Approval must be obtained from the IRB/EC and regulatory authorities (as locally required) before implementation of any changes, except for changes necessary to eliminate an immediate hazard to participants or any non-substantial changes, as defined by regulatory requirements.

#### 2.3.2. Publication Policy

The results of this study may be published or presented at scientific meetings. If this is foreseen, the Investigator agrees to submit all manuscripts or abstracts to the Sponsor for approval prior to submission. This allows the Sponsor to protect proprietary information and to provide comments based on information from other studies that may not yet be available to the Investigator.

The Sponsor will comply with the requirements for publication of study results. In accordance with standard editorial and ethical practice, the Sponsor will generally support publication of multicenter trials only in their entirety and not as individual center data. In this case, a coordinating Investigator will be designated by mutual agreement.

Any formal publication of the study in which contribution of Sponsor personnel exceeded that of conventional monitoring will be considered as a joint publication by the Investigator and the appropriate Sponsor personnel.

Authorship will be determined by mutual agreement and in line with International Committee of Medical Journal Editors authorship requirements.

Any inventions and resulting patents, improvements, and/or know-how originating from the use of data from this study will become and remain the exclusive and unburdened property of the Sponsor, except where agreed otherwise.

# 2.3.3. Dissemination of Clinical Study Data

A clinical study report containing the results of this trial will be made available to anyone who requests a copy. A description of this clinical trial and a summary of its results will be available at http://www.ClinicalTrials.gov.

### 2.3.4. Site Inspections

Site visits will be conducted by the Sponsor or an authorized representative for inspection of study data, participants' medical records, and eCRFs. The Investigator will permit national and local Health Authorities, Sponsor monitors, representatives, and collaborators, and the IRBs/ECs to inspect facilities and records relevant to this study.

### 3. ADMINISTRATIVE STRUCTURE

The Sponsor of the trial is F. Hoffmann-La Roche Ltd. The Sponsor is responsible for the study management, data management, statistical analysis and medical writing for the clinical study report.

# 4. STUDY AND SITE CLOSURE

The Sponsor (or designee) has the right to close the study site or terminate this study at any time. Reasons for terminating the study may include, but are not limited to, the following:

Participant enrollment is unsatisfactory.

The Sponsor will notify the Investigator and Health Authorities (if applicable) if the study is placed on hold, or if the Sponsor decides to discontinue the study or development program.

Study sites will be closed upon study completion. A study site is considered closed when all required documents and study supplies have been collected and a study site closure visit has been performed.

The Investigator may initiate study site closure at any time, provided there is reasonable cause and sufficient notice is given in advance of the intended termination.

Reasons for the early closure of a study site by the Sponsor or Investigator may include but are not limited to:

- Failure of the Investigator to comply with the protocol, the requirements of the IRB/IEC or local Health Authorities, the Sponsor's procedures, or GCP guidelines.
- Inadequate recruitment of participants by the Investigator.
- Discontinuation of further study treatment development.

# Appendix 2 Adverse Events: Definitions and Procedures for Evaluating, Follow-up and Reporting

#### 1. DEFINITION OF ADVERSE EVENTS

According to the E2A ICH guideline for Good Clinical Practice, an **adverse event** is any untoward medical occurrence in a participant or clinical investigation subject administered a pharmaceutical product and which does not necessarily have to have a causal relationship with this treatment.

An adverse event can therefore be-

 Any unfavorable and unintended sign (including an abnormal laboratory finding), symptom, or disease temporally associated with the use of a medicinal product, whether or not considered related to the medicinal product.

#### **Events Meeting the AE Definition:**

Adverse events that are related to a protocol-mandated intervention.

### Events **NOT** Meeting the AE Definition:

- Abnormal safety assessments which are associated with the underlying disorder, unless judged by the Investigator to be more severe than expected for the participant's condition.
- The disorder being studied or expected progression, signs, or symptoms of the disorder being studied, unless more severe than expected for the participant's condition.
- Medical or surgical procedure (e.g., endoscopy, appendectomy): the condition that leads to the procedure is an AE.
- Situations where an untoward medical occurrence did not occur (social and/or convenience admission to a hospital).
- Anticipated day-to-day fluctuations of pre-existing disorder(s) present or detected at the start of the study that do not worsen.

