#### 8.3 ADVERSE EVENT AND SERIOUS ADVERSE EVENT

The definitions of an AE or serious adverse event (SAE) can be found in Appendix 2. Only adverse events and serious adverse events caused by a protocol-mandated intervention should be reported (e.g., headache related to completion of the scales in this study).

The Investigator and any qualified designees are responsible for ensuring that all adverse events (including assessment of seriousness, severity and causality; see Appendix 2) are recorded on the Adverse Event eCRF and reported to the Sponsor in accordance with instructions provided in this section and in Appendix 2.

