# 2. DEFINITION OF SERIOUS ADVERSE EVENTS

If an event is not an AE per definition above, then it cannot be a serious adverse event (SAE) even if serious conditions are met (e.g., hospitalization for signs/symptoms of the disease under study, death due to progression of disease).

A serious adverse event is defined as any untoward medical occurrence (i.e., procedural-related):

Results in death.

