### 5. PREEXISTING MEDICAL CONDITIONS

A preexisting medical condition is one that is present at the screening visit for this study. Such conditions should be recorded on the General Medical History and Baseline Conditions eCRF.

A preexisting medical condition should be recorded as an adverse event only if the frequency, severity, or character of the condition worsens during the study and is related to study procedure(s). When recording such events on the Adverse Event eCRF, it is important to convey the concept that the preexisting condition has changed by including applicable descriptors (e.g., "more frequent headaches").

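### Appendix 2 excludes expected ASD symptoms from the AE and SAE definitions on severity alone, in conflict with the causality test in Section 8.3 and the worsening test in Appendix 3

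*Combined protocol and SAP*

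**What the plan says.** Section 8.3 sends the reader to Appendix 2 for the definitions and sets the reporting rule: "Only adverse events and serious adverse events caused by a protocol-mandated intervention should be reported". Appendix 2 Section 1 starts from the same test, giving as the events that meet the definition: "Adverse events that are related to a protocol-mandated intervention".

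The list of events that do not meet the definition follows. Two of its bullets are "The disorder being studied or expected progression, signs, or symptoms of the disorder being studied, unless more severe than expected" (for the participant in question) and "Anticipated day-to-day fluctuations of pre-existing disorder(s) present or detected at the start of the study that do not worsen". A further bullet excludes abnormal safety findings linked to the underlying disorder unless they are judged more severe than expected. None of the three mentions cause.

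Appendix 2 Section 2 extends the exclusion: "If an event is not an AE per definition above, then it cannot be a serious adverse event (SAE) even if serious conditions are met". Its examples are admission to hospital for symptoms of the studied disease and death from its progression.

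Appendix 3 Section 5 records a pre-existing condition as an AE only when two things hold: it has worsened in frequency, severity or character, and this is related to study procedures. Appendix 3 Section 4 requires every death in the reporting period to be recorded and reported at once, including one put down to the disorder.

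**The concern.** This is a non-drug study, so any harm can come only from the procedures: visits, interviews, questionnaires and devices. In participants with ASD, one plausible form of harm is a behaviour that already belongs to the disorder. The protocol itself treats self-injury as a repetitive behaviour seen in ASD: it is an RBS-R subscale (Section 8.1.1.9) and part of a CY-BOCS-ASD checklist category (Section 8.1.1.6). An exclusion that asks whether a symptom is expected, but not whether a procedure set it off, can remove an event that Section 8.3 asks sites to report.

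Two things are at stake. Sites may classify like events differently, depending on which passage they follow. And adverse events are the only endpoint in the safety analysis table (Table 5, Section 9.2.2). If procedure-triggered symptoms in the usual range are left out by definition, the AE summary cannot speak to them, and it is a weaker check on the statement in Section 2.2 that participation carries no risks.

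**Working it through.** The plan gives no figure on this point and no arithmetic applies. The check is to put the same event through each passage.

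| Event | Section 8.3 and 'Events Meeting the AE Definition' | Appendix 2 Section 1 exclusion | Appendix 3 Section 5 |
|---|---|---|---|
| A. ASD symptom set off by a procedure, at usual frequency, severity and character | AE, report | Not an AE | Not recorded (no worsening) |
| B. Procedure-related, more frequent or different in character, not more severe | AE, report | Not an AE (severity exception not met) | Recorded as AE |
| C. Procedure-related, more severe than expected | AE, report | Not excluded | Recorded as AE |
| D. Worse than expected, unrelated to any procedure | Not reported | Not excluded | Not recorded |

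**Row A.** Section 8.3 and the positive definition include the event. The exclusion list and Appendix 3 Section 5 leave it out.

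**Row B.** The two appendices disagree. More severe cannot simply be read as more frequent: Appendix 2 Section 3.1 explains severity as intensity, and Appendix 3 Section 5 names frequency and severity as separate features.

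**Row C.** All passages agree that the event is an AE.

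**Row D.** There is no conflict over reporting. Escaping an exclusion does not make an unrelated event reportable, because the Section 8.3 filter still applies.

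**What the exclusion adds.** Section 8.3 already keeps unrelated ASD symptoms out. Read together with it, the only further ASD events that the exclusion can remove are those a procedure caused, which are the events Section 8.3 wants. Section 8.3.6, on disease-related events that do not qualify as AEs or SAEs, is marked as not applying to this study, yet Appendix 2 applies such an exclusion. Appendix 2 Section 1 also still defines an AE by reference to a medicinal product, although Section 6 says none is given.

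**Step to SAEs.** An event in row A, or in row B under Appendix 2, is not an AE and so cannot be an SAE whatever its outcome. The hospitalisation example states neither the severity exception nor a condition on cause.

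**Deaths.** Under Appendix 2 Section 2, death from progression of the disease cannot be an SAE. Under Appendix 3 Section 4, a death attributed to the disorder goes on the AE form and to the sponsor immediately. A site cannot tell from the text which governs.

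**The case against.** The strongest reply is that the passages are cumulative filters and that aggravated behaviour is kept. Appendix 2 retains symptoms more severe than expected, its fluctuation bullet covers only those that do not worsen, and Appendix 3 Section 5 retains procedure-related worsening of three kinds. This stands. A reader might infer that all procedure-triggered distress or self-injury falls outside reporting; the documents do not support that. Nor do they support the inference that the severity exception brings unrelated worsening into reporting (row D).

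The SAE consequence is also narrow. An episode that leads to hospitalisation will usually be more severe than expected for that participant, so it stays an AE, and Appendix 3 Section 6 then makes it serious. An extra episode may also count as a change in frequency. Anxiety is described in the Introduction among co-morbid conditions and associated problems, so it is not plainly a symptom of the disorder under the exclusion.

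Two further inferences fail. The entry thresholds (CGI-S of at least 4, CY-BOCS-ASD of at least 12) do not show that self-injury or distress is expected in every one of about 90 ASD participants. And although Table 4 gives 182 to 232 minutes for a child's Baseline scales without RMET, 132 to 177 of these are completed by the caregiver or are a caregiver interview. That leaves 182 − 132 = 50 to 232 − 177 = 55 minutes, and a visit may be spread over two days. The total is not a measure of burden on the child.

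Finally, AEs are summarised descriptively, investigators ask about them at every contact (Section 8.3.1), and scale responses suggesting an AE are assessed (Appendix 3 Section 7). This limits the consequence but does not remove the conflict: the assessment in Appendix 3 Section 7 goes back to the same disputed criteria.

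**Conclusion.** The inconsistency is real and worth correcting, within limits. Following the Appendix 2 exclusion as written drops procedure-triggered ASD symptoms in the participant's expected range. It also contradicts Appendix 3 Section 5 for procedure-related symptoms that change in frequency or character without becoming more severe. Separately, the passages on death due to the disorder disagree.

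The size is unknown: the documents give no rate for such events and none can be derived. The conclusion assumes that sites read the exclusion list literally and treat behaviours such as self-injury as signs of ASD where they are already known in the participant. A site that gave the positive definition precedence would lose nothing, but the text does not say that it has precedence. No primary or secondary objective is affected. The effect is on the AE summary and on consistency between sites.

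**What to change.** Reconcile Section 8.3, Appendix 2 Sections 1 and 2, and Appendix 3 Sections 4 and 5:

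- **Appendix 2 Section 1.** In the bullets on findings linked to the underlying disorder and on symptoms of the disorder, keep the severity exception and add: *or considered caused by a protocol-mandated intervention*. The fluctuation bullet has no exception clause, so add the same words there introduced by *unless*.
- **Appendix 2 Section 2.** Add the same condition to the hospitalisation example.
- **Appendix 3 Section 5.** Align the wording so that rows A and B receive the same answer as under Section 8.3.
- **Deaths.** State one rule for death attributed to the disorder, and make Appendix 2 Section 2 and Appendix 3 Section 4 agree. The documents do not show which is intended.

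The cost is a few words in two appendices and a note for site training. Investigators would have to judge causality for some behaviours within the usual range, as Section 8.3 already implies. Some additional AE entries will follow; their number cannot be estimated from the documents.

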# 2. DEFINITION OF SERIOUS ADVERSE EVENTS

If an event is not an AE per definition above, then it cannot be a serious adverse event (SAE) even if serious conditions are met (e.g., hospitalization for signs/symptoms of the disease under study, death due to progression of disease).

A serious adverse event is defined as any untoward medical occurrence (i.e., procedural-related):

Results in death.

### Is life-threatening.

The term "life-threatening" in the definition of "serious" refers to an event in which the participant was at risk of death at the time of the event; it does not refer to an event which hypothetically might have caused death if it was more severe.

 Requires inpatient hospitalization or prolongation of existing hospitalization (see Appendix 3).

In general, hospitalization signifies that the participant has been detained (usually involving at least an overnight stay) at the hospital or emergency ward for observation and/or treatment that would not have been appropriate in the physician's office or outpatient setting. Complications that occur during hospitalization are AEs. If a complication prolongs hospitalization or fulfills any other serious criteria, the event is serious. When in doubt as to whether "hospitalization" occurred or was necessary, the AE should be considered serious.

Hospitalization for elective treatment of a pre-existing condition that did not worsen from Baseline is not considered an AE.

#### Results in persistent or significant disability/incapacity

Disability means substantial disruption of the participant's ability to conduct normal life functions.

This definition is not intended to include experiences of relatively minor medical significance such as uncomplicated headache, nausea, vomiting, diarrhea, influenza, and accidental trauma (e.g., sprained ankle) which may interfere with or prevent everyday life functions but do not constitute a substantial disruption.

Is a congenital anomaly/birth defect – not applicable for this study.

#### Other significant events:

Medical or scientific judgment should be exercised in deciding whether SAE reporting is appropriate in other situations such as important medical events that may not be immediately life-threatening or result in death or hospitalization but may jeopardize the participant or may require medical or surgical intervention to prevent one of the other outcomes listed in the above definition. These events should usually be considered serious.

# 3. RECORDING OF ADVERSE EVENT AND/OR SERIOUS ADVERSE EVENT

When an AE/SAE occurs, it is the responsibility of the Investigator to review all documentation (e.g., hospital progress notes, laboratory reports, and diagnostics reports) related to the event.

The Investigator will then record all relevant AE/SAE information in the CRF.

It is **not** acceptable for the Investigator to send photocopies of the participant's medical records to Medical Monitor in lieu of completion of the eCRF.

There may be instances when copies of medical records for certain cases are requested by Sponsor. In this case, all participant identifiers, with the exception of the participant number, will be redacted on the copies of the medical records before submission to Sponsor.

The Investigator will attempt to establish a diagnosis of the event based on signs, symptoms, and/or other clinical information. Whenever possible, the diagnosis (not the individual signs/symptoms) will be documented as the AE/SAE.

#### 3.1. ASSESSMENT OF SEVERITY

The Investigator will make an assessment of severity for each AE and SAE reported during the study and assign it to one of the categories provided in Table 1 (as a guidance for assessing adverse event severity).

The terms "severe" and "serious" are not synonymous. Severity refers to the intensity of an adverse event (rated as mild, moderate, or severe, or according to a pre-defined grading criteria [e.g., National Cancer Institute Common Terminology Criteria for Adverse Events [NCI CTCAE] criteria); the event itself may be of relatively minor medical significance (such as severe headache without any further findings).

Severity and seriousness need to be independently assessed for each adverse event recorded on the eCRF.

Serious adverse events are required to be reported by the Investigator to the Sponsor immediately (i.e., no more than 24 hours after learning of the event.

Table 1 Adverse Event Severity Grading Scale

Severity	Description
Mild	Discomfort noticed, but no disruption of normal daily activity
Moderate	Discomfort sufficient to reduce or affect normal daily activity
Severe	Incapacitating with inability to work or to perform normal daily activity

Note: Regardless of severity, some events may also meet seriousness criteria. Refer to definition of a serious adverse event (see above).

#### 3.2. ASSESSMENT OF CAUSALITY

Investigators should use their knowledge of the participant, the circumstances surrounding the event, and an evaluation of any potential alternative causes to determine whether or not an adverse event is considered to be related to the study mandated procedures, indicating "yes" or "no" accordingly. The following guidance should be taken into consideration:

- Known association of the event with the disease under study.
- Presence of risk factors in the participant or use of concomitant medications known to increase the occurrence of the event.

Presence of non-treatment-related factors that are known to be associated with the
occurrence of the event.

